4.1 Planned Duration of Study

Subjects enrolled in this study will fall into two categories that will determine the duration of the study. These include screening and the follow-up portion of the study.

- Open-label lead-in and Stage 1 only subjects: 14 months
- Stage 1 subjects who continue to Stage 2: 18 months

Table 2. Time & Events MP9 Stage 1	Screen/Baseline	Preparatory	Experiment	tal Session 1	Experimental Session 2		End of Stage 1
Visit #	Prior to Enrollment	V1, 2, 3	V4	V5, 6, 7	V8	V9, 10, 11	V12
Type of Visit	Baseline Screening may take place over more than one day up to one month prior to Visit 1	Preparatory Sessions	Experimental Session 1	Integrative Sessions	Experimental Session 2	Integrative Sessions	Follow-Up & Outcome
Visit Timing or Study day or Window		Approx. 1 week apart	3-5 weeks post V1	Approx. 1 week apart A	3-5 weeks post V4	Approx. 1 week apart ^A	May happen over more then 1 day. 2 months post V8
Informed Consent	X						
Medical/Psychiatric History	X						
General Physical Exam, ECG	X						
Brief Neurological Exam	X						
SCID	X						
Clinical Lab Tests, w/ HIV test	X						
Collect Concomitant Medication		X	X	X	X	X	X
Medication Taper (if applicable)	**	X	**		***		
Drug Screen	X		X		X		
Pregnancy Screen (if applicable)	X		X		X		
CAPS, GAF, BDI -II, PSQI (with Ind. Rater)	X						X
Study Enrollment after meeting I/E		X ^B					
Record to Audio/Video		X	X	X	X	X	
General Well-Being		X	X ^D	X	X D	X	X
Obtain Container Assignment from Randomization Program			X ^C		X ^C		
C-SSRS	X	X^{H}	X D, E, F	X ^J	X D, E, F	X ^J	X
Administer IP Drug + Therapy			X		X		
Monitoring of BP, Pulse and Temp.			X		X		
SUD			X ^{E, G}		X ^{E, G}		
Beliefs of Condition Assignment				Χ ^I		Χ ^I	
Overnight Stay			X		X		
PDS	X			X ^N		X ^N	X
Integrative Therapy Session				X		X	
7 days Integrative Telephone Contact				X ^J		X ^J	
AEs Requiring Medical Attention			X	X	X	X	X
Spont. Reactions and all AEs			X^{K}	X^{K}	X^{K}	X^{K}	
AEs related to changes in psychiatric status or withdrawal		X	X	X	X	X	X
Serious Adverse Events		X	X	X	X	X	X
Unblinding							X^{L}
RRPQ							X^{M}
Issue Memory Aid Card							X^{M}
	. D 0 1 177 1 1 0 1 1 1	241		1 1 61		E 1 1 1 1	

Table 3. Time & Events MP9 Stage 2	Preparatory	Experimen	Experimental Session 1 Experimental Session 2		ental Session 2	End of Stage 2		Long Term Follow-Up
Visit #	V13*	V14	V 15, 16, 17	V18	V 19, 20, 21	V22		1 Year Follow-up
Type of Visit	Preparatory Session	Experimental Session 1	Integrative Sessions	Experimental Session 2	Integrative Sessions	Follow-Up & Outcome		Follow-Up & Outcome
Visit Timing or Study day or Window	Within 1 month of V12*	1 week post V13	Approx. 1 week apart ^A	3-5 weeks post V14	Approx. 1 week apart ^A	May happen over more then 1 day. 2 months post V17	2	May happen over more then 1 day. One Year After V8 or V17
Confirm Informed Consent	X						že 7	
Confirm Inclusion/Exclusion	X						Stage	
Entry into Stage 2	X						Š	
Collect Concomitant Medication	X	X	X	X	X	X	or	X
Record to Audio/Video	X	X	X	X	X		e 1	
General Well-Being	X	X^{B}	X	XB	X	X	Stage	X
Drug Screen		X		X			r S	
Pregnancy Screen (if applicable)		X		X			after	
CAPS, GAF, PSQI, BDI-II (with Ind. Rater)	Use V12*					X	ာ ၁၈	X
C-SSRS	X	X ^{B, C, D}	X	X ^{B, C, D}	X	X	dn	X
Administer IP Drug + Therapy		X		X			ΜO	
Monitoring of BP, Pulse and Temp.		X		X				
SUD		X ^{C, E}		X ^{C, E}			Ĕ	
Overnight Stay		X		X			 	
PDS	Use V12*		X^{H}		X^{H}	X	Term Follow	X
Integrative Therapy Session			X		X		18	
7 days Integrative Telephone Contact			X ^F		X ^F		Long	
AEs Requiring Medical Attention	X	X	X	X	X	X		
Spont. Reactions and all AEs		X^G	X^G	X^G	X^G			
AEs related to changes in psychiatric status or withdrawal	X	X	X	X	X	X		X
Serious Adverse Events	X	X	X	X	X	X		X
RRPQ						X		
Issue Memory Aid Card						X		
Follow up Questionnaire								X
Termination Visit								X

^{*} Re-baseline if Visit 13 is more than 1 month from V12, then the measures from V12 will need to be repeated prior to starting Stage 2.

A = First Integrative session is 1 day after Exp. session B = Approximately 6 hours post MDMA C = At the beginning of the session D = As needed E=Approximately every 60 minutes F = For 7 days post Exp. Session, CSSRS D2 and D7 of calls only, General well being for all 7 days G= Spontaneously reported reactions will be collected on the day of MDMA administration and for seven days after each Exp. Session. H = Subjects will complete PDS on third integrative session only

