2.3 Protocol Purpose

This Phase 2 study is a randomized, double-blind study in 10 subjects comparing the effects of low and full dose MDMA as an adjunct to manualized psychotherapy. The first two subjects will be enrolled in the open label full dose lead-in. The remaining eight subjects will enroll in Stage 1 of the protocol and receive either an active placebo dose (low dose) or a fully active dose of MDMA during two experimental psychotherapy sessions, each lasting six to eight hours and scheduled three to five weeks apart. Five subjects will be randomized to the full dose and 3 subjects will be randomized to the active placebo dose of MDMA. The extent of PTSD symptoms will be assessed at baseline, and two months after the second experimental session by a clinician and throughout using a self-report measure. Subjects enrolled in Stage 1 who receive the active placebo will have the opportunity to enroll in Stage 2 of the protocol and complete open-label experimental sessions with the fully active dose of MDMA on the same schedule as Stage 1. Participants assigned to receive the full dose of MDMA will be assessed at 12 months after the second experimental session of Stage 1, and participants assigned to active placebo who enroll in Stage 2 will be assessed 12 months after the second Stage 2 experimental session. This study will allow comparison between the impact of active placebo and full dose MDMA on PTSD symptoms, and on symptoms of depression and sleep quality. This study will also permit the refinement of the treatment manual.

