In Stage 1, subjects will be randomly assigned to receive two experimental psychotherapy sessions assisted by either active placebo MDMA (3 subjects) or full dose MDMA (5 subjects). Subjects who receive the active placebo dose of MDMA will be offered the option to enroll in the open-label Stage 2 unless they meet any exclusion criteria for study participation. In Stage 2, subjects will receive full dose MDMA and the experimental sessions will otherwise follow the same sequence of events after a single preparatory session. (See Table 3 Time and Events)

All outcome measures will be assessed by a blinded independent rater. The independent rater will assess PTSD symptoms with the CAPS and PDS, quality of life with the GAF, symptoms of depression with the BDI-II, and sleep quality with the PSQI. The subjects will complete the PDS, a self-report measure of their PTSD symptoms, to provide correlations with measures administered by the independent rater. The PDS will be completed at baseline, during every third integrative session after an experimental session, and at the end of each Stage. Baseline assessments will be compared with assessments made in Stage 1.

All subjects will complete a follow-up occurring 2 months after their last experimental session in Stage 1 and Stage 2, if applicable. The blind will be broken for all subjects in Stage 1 after completing this assessment. In addition all subjects will complete a visit 12 months after their final experimental session where outcome measures and a questionnaire on any lasting benefits or harms of the treatment will be administered.

At each visit with the therapists, the subject's general wellbeing and suicidality will be assessed with the Columbia Suicide Severity Rating Scale (C-SSRS). Adverse Events and Concomitant Medications will be collected as described in Section 8.5 and 9.0 of the protocol.

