5.2.8 Open Label Stage 2 for Active Placebo Subjects

- a. Subjects will be reminded that participation in Stage 2 is voluntary and optional.
- b. Subjects who elect to enroll in Stage 2 will undergo the same course of therapy and evaluation as in Stage 1, but with full dose MDMA during two experimental sessions.
- c. Assessment of PTSD symptoms at the end of Stage 1 will serve as baseline assessments in Stage 2.
- d. If the start of Stage 2 is delayed for more than 30 days from the time of the last CAPS in Stage 1 to the first preparatory session in Stage 2 (Visit 13), the independent rater will re-administer the CAPS, PDS, BDI-II, GAF and PSQI, and these scores will be used as the baseline for comparison to assessment at the end of Stage 2.
- e. Subjects entering Stage 2 will meet with both therapists for a single review and preparatory psychotherapy session (Visit 13).
- f. Subjects will receive two open-label MDMA-assisted therapy sessions (V14, 18).
- g. Subjects will have the same sequence of sessions and integrative therapy as in Stage 1. Visits will be scheduled consecutively according to the Time and Events Table 3.
- h. Subjects will complete the PDS on the third integrative session.
- i. The same safety measures will be administered during Stage 2, including C-SSRS before, during and after each open-label session, vital signs and SUD during each open-label session.
- j. Spontaneously reported reactions, AEs and Medications will be collected and reported as described in Section 8.5 and 9.0 of the protocol.

5.2.9 Evaluation at the End of Stage 2

Treatment effects will be assessed at the end of Stage 2. This visit will consist of two meetings that may be completed on separate days, one with the independent rater and the other with the therapists.

- a. Subjects will meet the independent rater for at least an hour and a half.
- b. The blinded independent rater will administer:
 - CAPS to assess PTSD symptoms
 - PDS to assess self-reported PTSD symptoms
 - BDI-II to assess depression symptoms
 - GAF to assess general psychological function
 - PSQI to assess sleep quality

- c. After completing all assessments and measures with the independent rater, the subject will meet with the therapists for approximately 30 minutes.
- d. The therapists will assess suicidality with the C-SSRS.
- e. General wellbeing will be assessed.
- f. The subject will complete the Responses to Research Participation Questionnaire (RRPO).

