5.2.10 Long-Term Follow-up

All subjects who completed the lead-in, Stage 1 and Stage 2 will be evaluated for long-term effects 12 months after their last MDMA-assisted psychotherapy session. This visit will consist of two meetings, one with the independent rater and the other with the therapists.

- a. The independent rater will administer the CAPS, PDS, BDI-II, GAF and the PSQI.
- b. Subjects will have a final meeting with at least one of the therapists to review specified AEs and medications since the last visit. Subjects should bring the Memory Aid Cards to this visit, to be used as aids in recollection. These cards will not be collected. AEs and Medications will be collected as described in Sections 8.5 and 9.0 of the protocol.
- c. The therapists will assess suicidality with the C-SSRS.
- d. General wellbeing will be assessed.
- e. Subjects will complete a questionnaire assessing positive and negative long-term effects of the study.
- f. Subjects will complete the termination visit at this time.

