12.0 Data Analysis

The Sponsor will examine CAPS, PDS, BDI-II, GAF and PSQI scores at baseline and two months after the second experimental session at the end of Stage 1 in Active Placebo and Full Dose conditions with independent sample t-tests for baseline scores. When MDMA and Active Placebo scores are not significantly different at baseline, a second independent sample t-test will examine the scores at the end of Stage 1, with p. set at 0.05. Subsequent independent sample t-tests will be applied to scores where there are significant differences in baseline values, with p. set at 0.05.

A repeated measures analysis of variance (ANOVA) will be performed upon PDS scores at baseline, after the third integrative session (Visit 7), the sixth integrative session (Visit 11) and at the end of stage 1, with p. set at 0.05. Condition (active placebo or full dose MDMA) will serve as a between-subjects factor. PDS and CAPS scores will be correlated at baseline and at the end of Stage 1 to examine the degree to which the two measures arrive at similar symptom severity scores.

Formal statistical comparisons between Stage 1 and Stage 2 scores may only occur if all three eligible participants enroll in Stage 2. Lead-in subjects will be compared statistically to Stage 2 subjects, and data from lead-in subjects will only be utilized if they are equivalent to Stage 2 subjects. The sponsor will perform an analysis comparing CAPS and BDI-II scores after experimental and open-label sessions for participants in the full dose condition and another analysis for participants enrolled in Stage 2. Descriptive statistics will be computed for PDS scores for the end of Stage 1, the third and sixth integrative sessions of Stage 2 (Visits 17 and 21(and the end of 21. The sponsor will examine CAPS, PDS, GAF, BDI-II and PSQI scores 12 months after the final MDMA-assisted psychotherapy session. If there is enough data available for formal comparisons, the Sponsor will use a repeated measures ANOVA with baseline, end of Stage 1 and end of Stage 2 scores as repeated measure at p. set at 0.05.

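### Table 3 times the Stage 2 outcome visit and the Stage 2 subjects' one-year visit from V17, an integrative session, while the text times both from the last experimental session, V18

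*Protocol*

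**What the plan says.** Table 3 (protocol section 4.1, repeated in SAP section 5.0) gives the timing of V22 as "May happen over more then 1 day. 2 months post V17" and of the long-term follow-up as "One Year After V8 or V17".

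The same documents identify the visits:

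- Protocol 12.0 refers to "the third and sixth integrative sessions of Stage 2 (Visits 17 and 21"), so V17 is a non-drug session.
- Protocol 5.2.8(f) states: "Subjects will receive two open-label MDMA-assisted therapy sessions (V14, 18"). The last Stage 2 experimental session is therefore V18.

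The text uses a different starting point from the table:

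- Protocol 4.0, repeated in SAP 5.0: "All subjects will complete a follow-up occurring 2 months after their last experimental session in Stage 1 and Stage 2, if applicable".
- Protocol 2.3: "participants assigned to active placebo who enroll in Stage 2 will be assessed 12 months after the second Stage 2 experimental session".
- Protocol 5.2.10: subjects "will be evaluated for long-term effects 12 months after their last MDMA-assisted psychotherapy session".

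Table 2 times the matching Stage 1 visit, V12, at two months after V8. V8 is the second Stage 1 experimental session, so Table 2 agrees with the text.

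**The concern.** For V22 the conflict bears on how visits are actually booked. Protocol 5.2.8(g) says "Visits will be scheduled consecutively according to the Time and Events Table 3". Section 5.2.9, which describes V22, states no interval, whereas 5.2.7 does state one for V12. For the one-year visit, 5.2.10 does give a timing, so there the table simply contradicts the text. The V8 anchor in the same cell, for lead-in and Stage 1-only subjects, is consistent with the text.

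If a site schedules from Table 3, three things follow:

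1. Stage 2 outcomes are measured sooner after the last session than Stage 1 or lead-in outcomes. A difference in time since session then enters the Stage 1 versus Stage 2 comparison and the protocol's lead-in versus Stage 2 comparison.
2. Under protocol 8.5, collection of events requiring medical attention runs to the last two-month follow-up. It would close earlier after the last full-dose session in crossover subjects than in the others.
3. If V22 follows the table but the one-year visit follows 5.2.10, the change from End of Stage 2 to follow-up in SAP 9.9.2.1 spans a longer interval than the change from End of Stage 1 to follow-up in the full dose group.

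**Working it through.** The documents state no figure for the gap between V17 and V18, so there is none to reproduce. It can be derived from the Table 3 windows.

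**Inputs**

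- V15: one day after V14 (Table 3, note A).
- V15, V16 and V17: about one week apart (Table 3); taken as 7 days.
- V18: 3 to 5 weeks after V14 (Table 3), that is day 21 to 35.
- Stage 2 subjects: three at most (protocol Table 5).
- Assumptions: two months = 61 days; one year = 365 days.

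**Gap between the two anchors, with V14 as day 0**

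- V17 = 1 + 7 + 7 = day 15.
- Gap = V18 − V17 = 21 − 15 = 6 days, up to 35 − 15 = 20 days. At a 4-week interval it is 28 − 15 = 13 days.

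**V22, counted from V18**

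- By the text: 61 days.
- By the table: 61 − 6 = 55 days, down to 61 − 20 = 41 days. This is short by 6/61 = 10% to 20/61 = 33%.

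**One-year visit, counted from V18**

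- By the text: 365 days.
- By the table: 365 − 6 = 359 days, down to 365 − 20 = 345 days. This is short by 1.6% to 5.5%.

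**Mixed case: V22 by the table, one-year visit by 5.2.10**

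- End of Stage 2 to follow-up: 365 − 55 = 310 days, up to 365 − 41 = 324 days.
- End of Stage 1 to follow-up in the full dose group: 365 − 61 = 304 days.
- Excess: 6/304 = 2.0% to 20/304 = 6.6%.

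**Sensitivity to the integrative-visit spacing**

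| Spacing | V17 (day) | Gap to V18 (days) | V22 after V18 (days) |
|---|---|---|---|
| 6 days | 13 | 8–22 | 39–53 |
| 7 days | 15 | 6–20 | 41–55 |
| 8 days | 17 | 4–18 | 43–57 |

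Over all three spacings the gap is 4 to 22 days and V22 falls 39 to 57 days after V18.

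**Would a site notice?** Not necessarily. V21 falls about day 15 after V18, so a V22 timed from V17 still comes after V21 and the visit order looks normal.

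**Does the planned duration settle the anchor?** Protocol 4.1 gives 18 months for Stage 2 subjects. Add the following, in days: screening 0–30, V1 to V4 21–35, V4 to V8 21–35, V8 to V12 61, V12 to V13 0–30, V13 to V14 7, V14 to V18 21–35, and one year 365. The total is 496 to 598 days, or 16.3 to 19.6 months at 30.44 days per month. Counting the year from V17 instead gives 490 to 578 days, or 16.1 to 19.0 months. Both ranges contain 18 months, so the stated duration does not discriminate.

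**The case against.** The best reply is that this is a visit-number slip whose intended reading is plain. The narrative in both documents counts from the last experimental session, Table 2 does the same for V12, and nothing in the text supports V17. Protocol 5.2.8(b) asks for the same evaluation as in Stage 1, and 4.0 times the Stage 2 follow-up explicitly. The SAP describes its design section as a summary and defers to the protocol, so its copy of the table schedules nobody.

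The consequences can also be played down:

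- The Stage 1 versus Stage 2 comparison is conditional on all three eligible subjects enrolling in Stage 2. It is exploratory, and already confounded by order and open-label dosing.
- SAP 9.0 amends the protocol's analysis plan, and the SAP does not carry forward the lead-in versus Stage 2 comparison. It only adds the lead-in subjects to the 125 mg group in SAP 9.9.3.
- Under protocol 8.5, serious events, events leading to withdrawal and psychiatric-status events are collected throughout, and all adverse events are collected for seven days after each session. Only non-serious, non-psychiatric events needing medical attention could be lost.
- Twenty days is the extreme of the range; 13 days is the figure at a 4-week interval.

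These points limit the impact, and most of them stand. In particular, the lead-in versus Stage 2 consequence rests on the protocol alone. They do not remove the conflict: 5.2.8(g) names Table 3 as the scheduling source, 5.2.9 gives no interval to check it against, and the document to which the SAP defers contains the same contradiction.

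**Conclusion.** The contradiction is certain: the same two cells in both documents disagree with the text of both. Its effect is conditional and small. It arises only if a site books from Table 3, reaches at most three of ten subjects, and leaves the primary endpoint (baseline to V12, timed from V8) untouched.

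Where it does arise, and on the spacing and month-length assumptions given, V22 moves from about 61 to 41–55 days after the last experimental session. Collection of events requiring medical attention ends the same 6 to 20 days early. The one-year visit, if also taken from the table, shifts by about 2% to 5%. With so few Stage 2 subjects, a single mistimed visit is a third or more of the Stage 2 data. It should be corrected, but it does not threaten the trial's main result.

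**What to change.** Reconcile the V22 and long-term follow-up timing cells of Table 3, in the protocol and in the SAP, with the text, so that both Stage 2 assessments are counted from the event the text names, as V12 is counted from V8. Stating the interval in protocol 5.2.9, as 5.2.7 already does for V12, would close the gap there.

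For any subject already scheduled from V17, report the actual number of days since the last experimental session beside the Stage 2 and 12-month results.

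The cost is a minor amendment to two table cells in each document, plus one sentence if 5.2.9 is completed. It adds no visits and changes no analysis.

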4.2 Recruitment and Subject Population

Participants may be men or women aged 18 or older with a confirmed diagnosis of chronic PTSD who have undergone at least one treatment for PTSD without achieving remission. Prior treatment can include psychotherapeutic or pharmacological treatments, and people who have undergone one or more prior treatments are eligible for study participation. Subjects would not be excluded for having more than one traumatic event. Subjects must have a CAPS score equal to or greater than 50 and must meet all inclusion criteria and no exclusion criteria at baseline. Participants must be in good physical health and without major medical disorders that might affect the safety or tolerability of MDMA. Participants will be recruited through printed ads, internet ads, referrals from other psychiatrists, psychotherapists or physicians, through the Israeli Defense Forces (IDF) and through word of mouth. The first ten participants who meet all inclusion criteria without meeting any exclusion criteria will be admitted to the study. All recruitment materials and advertisements will be approved by the institution's IRB/EC.

4.2.1 Inclusion Criteria

Individuals eligible to be enrolled into this protocol are subjects who:

- 1. Meet DSM IV criteria for chronic PTSD with a duration of at least six months. Participants may have experienced one or more traumatic event;
- 2. Have a CAPS score of 50 or higher, indicating moderate to severe PTSD symptoms;
- 3. Have had at least one unsuccessful attempt at treatment for PTSD:
 - a. Treatment with a selective serotonin uptake inhibitor (SSRI), mirtazapine, a Serotonin Norepinephrine Reuptake Inhibitor (SNRI) or a monoamine oxidase inhibitor (MAOI)
 - b. Any form of psychotherapy for the treatment of PTSD:
- 4. May have a concurrent affective disorder, excepting bipolar affective disorder 1;
- 5. Are at least 18 years old;
- 6. If in ongoing psychotherapy at the time of recruitment, are able to continue to see their outside therapist during the course of the study. Subjects must sign a release permitting the investigators to communicate directly with their therapist.
- 7. May not change therapists, increase the frequency of therapy or commence any new type of therapy until after the evaluation session at the end of Stage 1 or 2, as applicable;
- 8. Are willing to refrain from taking any psychiatric medications during the study period, with the exception of gabapentin when prescribed for pain control. Any psychiatric drugs will be tapered in an appropriate fashion to avoid withdrawal effects. Medications will only be discontinued after consultation with the prescribing physician.
- 9. Agree to, for one week preceding each experimental session:
 - a. Refrain from taking any herbal supplement (except with prior approval of the research team)

- b. Refrain from taking any nonprescription medications (with the exception of non-steroidal anti-inflammatory drugs or acetaminophen unless with prior approval of the research team)
- c. Not take any prescription medications (with the exception of birth control pills, thyroid hormones or other medications approved by the research team) Note: Must have physician's approval;
- 10. Agree to take nothing by mouth except alcohol-free liquids after 24:00 (midnight) the evening before the experimental session;
- 11. Agree to refrain from the use of any psychoactive drug, with the exception of caffeine or nicotine, within 24 hours of each experimental session;
- 12. Agree not to use caffeine or nicotine for 1 hour before and 3 hours after ingesting the drug, or until the therapists deem it safe to do so;
- 13. Are willing to commit to medication dosing, experimental sessions, follow-up sessions and to complete evaluation instruments;
- 14. Are willing to remain overnight at the study site after each experimental session until after the integrative session occurring the next morning;
- 15. Are willing to be driven home the morning after the experimental sessions, after the integrative therapy session either by a driver arranged by the subject or by the site personnel or taxi;
- 16. Are willing to be contacted via telephone on a daily basis by one of the therapists for a week after each experimental session;
- 17. Are willing to refrain from participating in any other clinical trial for the duration of this clinical trial, including the follow up period;
- 18. If female subjects of childbearing potential, must have negative pregnancy test results, be willing to have pregnancy tests and must agree to use an effective form of birth control;
- 19. Are proficient in speaking and reading Hebrew;
- 20. Agree to have all psychotherapy sessions recorded to audio/video.

